7.1.2 Procedures to monitor subjects for safety or minimize risks

The proposed research is a low-risk behavioral trial. Study staff will be available to participants who have any difficulty with their equipment or any unexpected reaction during the intervention period. Study staff will be required to report all unanticipated events to the Northwestern University's IRB within 24 hours of knowledge or notification. All reportable new information will be reported to Northwestern University's IRB within 5 business days of knowledge or notification. Study staff members are also responsible to report all such events to the study PI as well. The study staff will monitor the progress of the trial and safety of participants on an ongoing basis. The procedures of this study will ensure discussion and reporting of all possible outcomes including unanticipated adverse events. If the adverse event is due to the intervention and is unexpected, the PI will draft a safety report and send a copy to Northwestern University's IRB. The IRB committee will serve as an objective review mechanism. This policy/procedure means that any potential conflict of interest inherent in the PI being the sole reviewer of these events is avoided.

We will use screening procedures to assess depression/suicidality. If risk of suicidality or severe depression is revealed, the PI will contact the participant the same day, taking emergency steps and making referrals as needed.

7.2.1 Procedures performed to lessen the probability or magnitude of risks

Please see the Data Safety and Monitoring Plan in Section 10.0 for procedures taken to lessen the probability or magnitude of risks.

7.2.2 Source records used to collect data about subjects.

PROTOCOL TITLE: Treating cognitive impairments in cancer patients via systematic light exposure

Data about subjects will be collected from medical charts, interview questions, questionnaires, blood samples, and output from the equipment (i.e., actigraph data and integrated meter data from the light boxes). Questionnaires will be administered in person and via an online portal (RedCap).

Participants who self-refer will be provided a release of information to access their medical chart from other institutions.

All data collected through RedCap will be coded to each subject's unique study ID. Any identifiable information will be coded in RedCap as an "identifier." This allows the study team to export ONLY deidentified data, whilst preserving the ability to run the study effectively (i.e., being able to access participant contact information and recording study-related communications). Redcap will not log the participants' IP addresses. Surveys, scripts and data collection forms are attached.

7.3 Data to be collected

Measures

- 1) **Background Information (Screening and Time 1):** Sociodemographic data regarding gender, age, ethnicity, religion, income, marital status, employment status as well as questions about inclusion/exclusion criteria will be gathered during the screening assessment and any changes in information will be gathered at subsequent assessments. Medical data will be gathered through medical chart review and interview including comorbid and excluded medical conditions, medical information related to transplant, current prescription sleep-related and non-sleep-related medications, history of treatment with light therapy, and remaining exclusion criteria. The Self-administered Comorbidity Questionnaire will be used to capture comorbid conditions and the Valdimarsdottir Infection Scale will be used to capture recent infections. Recent Changes in Care will be evaluated by asking questions about any changes in medical treatment in Times 2 and 3 assessment time points.
- 2) **Active Psychosis (Screening):** The 6-item Paranoia/Psychoticism Screener (PPS) based on the "Psychotic Symptoms" module of the Structured Clinical Interview for DSM-IV-TR Axis I Disorders (SCID)⁴⁵ that has good discriminant validity will be used to exclude participants with active psychosis.
- 3) **Suicidality (Screening):** Participants will be asked questions regarding suicidal ideation, including one item from the Brief Symptom Inventory (BSI),⁴⁶ "Over the last week, have you had thoughts of ending your life" that will be used to screen for active suicidal ideation. Additional questions will be asked to assess for active suicidality. Those who are actively suicidal will be referred for further assessment and treatment, and their physician and/or a psychosocial staff member will be contacted. The PI will also follow up with the participant.
- 4) **Substance Abuse (Screening):** Current substance abuse (not including tobacco use) will be assessed by combining the 4-item Rapid Alcohol Problems Screen (RAPS-4)⁴⁷ with the Two-Item Conjoint Screening (TICS)⁴⁸. Questions endorsed will be followed up with additional questions to determine alcohol or drug abuse/dependence. Both measures have good sensitivity and specificity.^{47, 48} Participants determined to have probable current substance abuse disorder will be ineligible for the study and referred for further assessment and treatment.
- 5) **Cognitive Screening (Screening):** Participants will be asked whether they have concerns about their cognition by asking a question derived from the two cognitive questions on the

PROTOCOL TITLE: Treating cognitive impairments in cancer patients via systematic light exposure

European Organization for Research and Treatment of Cancer Quality of Life Questionnaire (EORTC QLQ C-30).

- 6) **Neuropsychologically-assessed Cognitive Functioning (Times 1, 3, and 4):** Standardized neuropsychological tests will be used to evaluate multiple cognitive domains. They include all of the tests recommended by the International Cognition and Cancer Taskforce in their Lancet article⁶ chosen due to their frequent use in CRCI assessment and appropriateness for repeat assessments over time: a) Premorbid Intellectual Function will be assessed using the Wechsler Test of Adult Reading and the Vocabulary subtest of the Wechsler Adult Intelligence Scale - 4th Ed. (WAIS-IV) at Baseline only; b) Psychomotor vigilance will be assessed with the Psychomotor Vigilance Task; c) Attention will be assessed with the Digit Span subtest of the WAIS-IV;⁹⁹ d) Visual motor performance will be assessed with the Grooved Pegboard Test and Block Design subtest of the WAIS-IV; e) Visuospatial ability will be assessed with the Rey Complex Figure Test. f) Sustained attention and vigilance will be assessed with the Conners Continuous Performance Test 3rd Edition will be used to assess sustained attention and vigilance; g) Information processing will be assessed with Trail-Making Test A.¹⁰⁰ h) Processing speed will be measured with the Coding subtest of the WAIS-IV; i) Verbal fluency will be assessed with the Verbal Fluency subtest of the Delis-Kaplan Executive Function System (D-KEFS). j) Verbal learning and Memory will be assessed with the Hopkins Verbal Learning Test - Revised.¹⁰² k) Visual learning and memory will be assessed with the Brief Visuospatial Memory Test – Revised. l) Executive Function will be assessed with Trail-Making Test B¹⁰⁰ and the Paced Auditory Serial Addition Task¹⁰³ and the Stroop Color and Word Test.
- 7) **Subjective Cognitive Function (Times 1, 2, 3, and 4):** The Cognitive Failures Questionnaire is a 25-item self-report measure of cognitive difficulties in everyday life using a 5-point Likert scale. Its reliability and validity are well-documented. Those who score ≥ 43 are deemed to have clinically significant impairment. This measure has been used widely in the measurement of cognitive assessment, including for cancer-related cognitive impairment (e.g., Calvio, Peugeot, Bruns, Todd, & Beuerstein, 2010; Scherling, Collins, MacKenzie, Lepage, Bielajew, & Smith, 2012). Patient Assessment of Own Functioning Inventory – a 33-item self-report measure of a patient's self-perceptions regarding their functioning in everyday tasks and activities.
- 8) **Neurobehavioral functioning (Times 1, 2, 3, and 4):** The Frontal Systems Behavior Scale is a reliable and valid measure of neurobehavioral functioning (Grace & Malloy, 2001)
- 9) **Sleep Quality (Times 1, 2, 3 and 4):** The Pittsburgh Sleep Quality Index consists of 19 self-rated items (35). Scale reliability is excellent using both an internal consistency criterion (Cronbach's alpha = 0.83) and test-retest reliability ($r = 0.85$). The validity of the instrument is based on its ability to discriminate patients (those having either sleep problems and/or depressive symptoms) from controls (healthy participants without sleep complaints).
- 10) **Chronotype (Time 1):** The Morningness-Eveningness Questionnaire: A reduced scale (MEQr) will be used to collect data on baseline circadian predispositions (Horne & Ostberg, 1976; Adan & Almirall, 1991). It is a 5-item self-rated survey designed to measure whether a person's peak alertness is in the morning or evening. This measure takes approximately 1 minutes to complete.
- 11) **Physical health (Time 1):** Physical health measures will be included as covariates in data analyses as they have been shown to be associated with fatigue, sleep, depressed

PROTOCOL TITLE: Treating cognitive impairments in cancer patients via systematic light exposure

mood, and cognition.⁵⁷⁻⁶⁶ We will include Body Mass Index (a measure of adiposity) calculated by dividing a participant's weight by the square of their height. The World Health Organisation classifies a body mass index of 25-29.9 as overweight, 30-34.9 as obese class I, 35-39.9 as obese class II, and ≥ 40 as obese class III.

17) Usage (during light exposure): To measure adherence and fidelity to the procedures, the integrated meter in the Litebooks® record time and duration the light box turned on each day. Participants will also record when they turn on and off the light box and reasons for non-participation in a Litebook Log.

18) Actigraphy (Times 1, 3, and 4): Sleep/wake activity and CAR will be recorded with the Actiwatch-2 (Mini Mitter /Phillips/Respirronics), which is similar in size to a watch and worn on the nondominant wrist. Total sleep time, percent sleep, total wake time, number of awakenings per night, length of awakenings at night, percent awake, and napping behavior (number of naps; naptime) will be computed. The actigraph also records light and amount (lux) and duration (above 1000 lux) of light exposure. Each participant will wear the actigraph for 7 consecutive days at each of the 3 time points and complete a sleep log on which they will record time to bed, time awake and other information to be used in

PROTOCOL TITLE: Treating cognitive impairments in cancer patients via systematic light exposure

editing and scoring the data. For CAR, the activity data will be fit to an extended cosine model¹⁰⁹ from which circadian variables will be computed: acrophase (time of maximum modeled activity), amplitude (difference between maximum and minimum activity), mesor (mean of the modeled activity curve), and pseudo F-statistic (measure of rhythm robustness). There was no evidence of phase advance in [name]'s data, but we will control for it statistically if it exists.

19) Inflammatory immune markers (Times 1 and 3): The BMHO Laboratory will conduct an assessment of cytokines to examine cellular responses to antigen/mitogens and RNA for genetic molecular analysis. Venous blood will be used to assay proinflammatory and anti-inflammatory cytokines from serum using ELISA, and cytokine gene transcripts. Blood samples will be collected at Times 1 and 2. 11mL of blood will be collected for serum and intracellular RNA collection. Venous blood is collected into evacuated tubes containing serum-separating gel for serum and the PAXgene Blood RNA tube for intracellular RNA. To control for diurnal variation, samples will be collected in the morning whenever possible and processed immediately in the Biopsychosocial Mechanisms and Health Outcomes (BMHO) Program's wet lab using established blood processing protocols, or will be processed immediately in Northwestern's Clinical Research Unit CORE laboratory using established blood processing protocols, depending on the availability of the BMHO Program's lab technician. Drawn blood from participants will be brought to The Robert H. Lurie Comprehensive Cancer Center of Northwestern University by trained and certified lab staff under the supervision of the Office for Research Safety at Northwestern University. Blood will be processed using standard procedure to obtain serum. Bio-samples will be aliquoted and stored at -80°C for maximum preservation until assayed. All processing and assays will be carried out at The Robert H. Lurie Comprehensive Cancer Center of Northwestern University. Evaluation of cytokines in serum will be performed using commercial ultrasensitive solid phase ELISA kits, following the manufacturer's protocol. A ratio of pro- to anti-inflammatory cytokines will be derived as an indicator of immune dysregulation. Molecular testing of intracellular RNA via RT-PCR will be processed using the PAXgene Blood RNA Kit under the manufacturer's protocol. IL-6, IL-8, and IL-10 will be assayed by High Sensitivity Multiplex assay. IL-1ra and sTNF-RII will be measured using enzyme-linked immunosorbent assay (ELISA) analysis. Monoplex will be used for CRP measurement. Assays will be performed in batch format to minimize experimental variation. Molecular testing of intracellular RNA via RT-PCR will be processed using the PAXgene Blood RNA Kit under the manufacturer's protocol.

8.0 Data and Specimen Banking

8.1 Data or specimen storage and access

Participants will be assessed using blood samples collected by trained phlebotomists at two time points: within one week before initiation of the systematic light intervention (Time 1), and during the fourth week of the intervention (Time 2). As indicated in Section 8.3 above, serum and intracellular RNA samples will be stored at -80°C at The Robert H. Lurie Comprehensive Cancer Center of Northwestern University, or at the Northwestern Clinical Research Unit CORE laboratory. The facilities at The Robert H. Lurie Comprehensive Cancer Center or at the Northwestern Clinical Research Unit CORE laboratory will perform the assays on the biosamples. Assays will occur within the project period, which is 4.5 years. Only research team

PROTOCOL TITLE: Treating cognitive impairments in cancer patients via systematic light exposure

members, lab staff in the BMHO wet lab, lab staff in the Northwestern Clinical Research Unit CORE lab, and approved staff at The Robert H. Lurie Comprehensive Cancer Center will have access to the samples for the purposes of storage and assay only.

All paper-and-pencil research data (from questionnaires and interviews) will be stored in a locked file cabinet and identified by number only. Consent forms and tracking data (e.g., contact information) will be kept separately. Only study personnel will have access to the data.

Data from the RedCap online tool will be accessible to research study team members only with the following exceptions: All questionnaire data collected via RedCap will be linked to a subject's unique code – but no other identifying information will be accessible via this program.

Electronic research and tracking data will be stored on a secured Northwestern University network drive. Records for the study will be retained for at least 6 years after the investigation is completed and accessible only to study personnel. Upon completion of the study, the data files will be fully anonymized and the links between patients to the codes will be deleted.

8.2 Data to be stored or associated with each specimen

See Section 8.1 above.

8.3 Procedures to release data or specimens

Only anonymized data in SPSS format will be released to collaborators upon request and with the permission of the PI. Such data will not be identifiable to others.

9.0 Data and Specimen Management

9.1 Data analysis plan

Descriptive statistics will be calculated for the entire group and separately for each treatment group. T-tests and Fisher's exact tests will be used to assess group differences at baseline for possible confounders (i.e., demographic variables, and clinical characteristics *including time since transplant*). Variables showing differences between the two groups will be used as covariates in subsequent analyses. Since there is no known seasonality effect on cognitive functioning, seasonality will not be controlled in these analyses.

Aim 1: Assess the feasibility and acceptability of BWL as an intervention for CRCI in HSCT survivors. Feasibility: We will adhere to currently accepted practice for feasibility studies¹¹⁰ by measuring the number of eligible patients, willingness of participants to be randomized, follow-up rates, the number who cease the intervention and their specific concerns about the intervention. We will monitor adherence by examining integrated meter data (i.e., time and duration of light box use). We expect high adherence, but if there is variation in duration, we will use duration as a predictor of the outcomes. Participants will be asked to log light box use (beginning and ending time) and reasons for not using it if that occurs. There is no gold standard for what constitutes a “feasible” study and relevant CRCI intervention feasibility studies have not been home-based.^{18, 111} Nevertheless, in an inpatient cognitive rehabilitation study of HSCT patients, 78% completed baseline, intervention, and time 2 assessments.¹⁸ A light exposure feasibility study for seasonal affective disorder deemed a 68% completion rate as acceptable,¹¹² and this is the criteria we will use in this study. In [name]'s pilot study, breast cancer

PROTOCOL TITLE: Treating cognitive impairments in cancer patients via systematic light exposure

patients used the light box about 50% of the required days. This usage frequency was sufficient for cognitive improvement to occur in the BWL group. A 50% level of adherence will be considered acceptable in this study. Acceptability: As recommended in the literature, in addition to accrual rates, we will assess acceptability by evaluating participants' comments about the intervention after they have had experience with it.¹¹³ Finally, a comparison of the BWL and DRL on the FACIT-TS-G will be conducted using t-tests. Significant differences in favor of the BWL condition are expected.

Aim 2: Examine whether BWL compared with DRL among HSCT survivors suffering from cognitive impairment yields significant improvements in cognitive functioning. We will examine the cognitive functioning subscales and composite scores in separate analyses. Linear mixed model analysis with repeated measures will be conducted using the SAS procedure MIXED.

Contrasts will compare groups across assessments. The linear mixed model approach has a range of choices for the error variance/covariance structure and accommodates missing data thus protecting against a "completers only" bias. Since multiple outcomes will be correlated with one another, *p*-values for significance will be Sidak-adjusted for multiple comparisons. If there is variation in light box utilization, we will use duration time as a predictor of the outcome measures as in Aim 1. No pre-intervention bias favoring BWL over DRL is anticipated. However, we will test this assumption by crossing expectancy with the treatment condition. This interaction is not expected to be significant. These results will determine preliminary efficacy and sustainability of the intervention.

Power: Based on [name]'s pilot study with 10 breast cancer patients, the effect size indicated that we would need a sample size of 19 to achieve power at 0.80. However, the sample size is likely too small to provide reliable estimates of improvement in cognitive functioning. One of the main aims is to determine preliminary efficacy of the intervention in preparation for a larger scale trial. For a total sample of 80, we calculated the mean difference between the two treatment arms for the Neurocognitive (composite) Index and assumed a repeated measures design with an autoregressive lag 1 error structure and autocorrelation of 0.60. The difference able to be detected with power equal to 0.80 and alpha = 0.05, is 0.209.

Aim 3: Examine whether BWL compared with DRL affects sleep and psychological variables (depressed mood, fatigue) which have been implicated as correlates of cognitive functioning in cancer patients. Hypothesis 2: Sleep quality and psychological variables will improve in the BWL group compared to the DRL group. The Aim 1 analytic strategy will be used in the analysis of this aim. Power: Our preliminary R-21 study that examined BWL vs. DRL on cancer-related fatigue in a mixed cancer population (including HSCT) provided guidance for the power. Sleep Quality: While survivors in the BWL group had better sleep quality scores than the DRL group, the main effect for treatment was not statistically significant, no doubt due to sample size. Cohen's *d* was 0.63. For a repeated measures design with alpha equal to 0.05 and a sample size of 40 per group, power=0.99. CAR: There was significant time x treatment interaction (*p*=0.02) on the F statistic. We calculated power for a repeated measures design with autoregressive lag 1 structure and autocorrelation of 0.60. With alpha equal to 0.05 and sample size of 40 per group, power=0.99. Fatigue: As with CAR, there was significant time x treatment interaction (*p*=0.003). Using the same method as above, power = 0.99. Depressed mood: There was a significant (*p*=0.004) time x treatment interaction. Using the same method as above, power = 0.99.

Exploratory Aims: Explore a) whether BWL compared with DRL affects biological (inflammatory immune response) variables; and b) whether the effects of BWL compared to

PROTOCOL TITLE: Treating cognitive impairments in cancer patients via systematic light exposure

DRL on cognitive functioning are mediated by sleep, chronobiological factors (i.e., circadian activity rhythms), biological factors (i.e., inflammatory immune response), and psychological factors (i.e., fatigue, depressed mood).

- a) Assess whether the BWL intervention affects biological factors (IL-1ra, IL-6, IL-8, IL-10, sTNF-III, CRP, PBMCs, and intracellular RNA) that have been identified as correlates of CRCI. Biological variables will be measured at Times 1 and 2. The mixed linear model approach described in Aim 2 will be used here.
- b) The results of Aim 2 will provide evidence that BWL reduces cognitive impairment. Mediation analyses using bootstrapping will provide estimates of the effect of light treatment on the mediators, the effect of the mediators on cognitive functioning, the direct effect of light treatment on cognitive functioning, and the indirect effect of light treatment on cognitive functioning whilst accounting for the mediators. Advantages of this method include: 1) it does not rely on the causal steps approach to mediation analysis;^{114, 115} 2) bootstrapping of the sampling distribution does not rely on the assumption of normal sampling distributions of the indirect effects; 3) type II error is reduced because it requires fewer inferential tests; and iv) multiple mediators can be tested at once;¹¹⁶ 4) allows for statistical control of covariates. For this exploratory analysis, we will examine each category of factors as mediators separately (i.e., sleep, chronobiological, biological, and psychological factors).

Missing data: We will be using a mixed linear model using a maximum likelihood approach to parameter estimates which means that not every participant has to provide full data.

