1.2 Hypotheses

- Hypothesis 1: BWL treatment will be feasible and acceptable in autologous and allogeneic HSCT survivors.
- Hypothesis 2: Auto-HSCT and allo-HSCT survivors receiving BWL will have greater improvement in cognitive functioning than those receiving DRL.
- Hypothesis 3: The relationship between BWL and CRCI will be mediated by CAR and sleep.

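### Baseline covariates are chosen by tests between randomised arms with no threshold, and the Aim 2 contrast and handling of the Time 1 score are not stated

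*Combined protocol and SAP*

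**What the plan says.** Section 9.1 (Data analysis plan) opens with baseline comparisons: t-tests and "Fisher's exact tests will be used to assess group differences at baseline for possible confounders". The candidates are demographic variables and clinical characteristics, of which only time since transplant is named. It continues: "Variables showing differences between the two groups will be used as covariates in subsequent analyses". Neither a p-value nor a size of difference defines a difference for this purpose.

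Section 7.3, item 11, takes another route: "Physical health measures will be included as covariates in data analyses", because of their known association with cognition and related outcomes. BMI is the measure named. Sections 7.3 and 9.1 do not refer to each other on this.

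For Aim 2, section 9.1 specifies a linear mixed model and says "Contrasts will compare groups across assessments". It names no visit and does not say how the Time 1 score enters. Hypothesis 2 (section 1.2) is that BWL survivors "will have greater improvement in cognitive functioning than those receiving DRL". The power text in section 9.1 says "we calculated the mean difference between the two treatment arms for the Neurocognitive (composite) Index". It takes AR(1) errors, with 0.60 as the correlation between adjacent visits.

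**The concern.** In a randomised comparison, a baseline difference between arms is due to chance. Testing for it says nothing about whether the variable predicts the outcome, and prediction is what makes a covariate useful. The rule therefore leaves out real predictors in most trials and sometimes brings in irrelevant variables. With no threshold, the adjusted model is not known until the arms have been compared.

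How much this matters depends on the contrast. A covariate that enters only as a main effect cancels from a change score but not from a Time 1-adjusted comparison. Since the plan fixes neither the contrast nor the handling of Time 1, the cost of the rule cannot be read from it. The Aim 2 estimate is meant to prepare a larger trial, so its definition and adjustment set should not be open when the arms are first compared.

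**Working it through.** **Inputs from the document.** 40 per group, total 80, alpha 0.05 and AR(1) autocorrelation 0.60 (section 9.1). Neuropsychological tests at Times 1, 3 and 4 (section 7.3, item 6). A 68% completion criterion (section 9.1, Aim 1). About 180 autologous and 54 allogeneic transplants a year (section 17.2).

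**Assumptions.** SD 1; two-sided test; visits equally spaced; effect 0.5 SD at Times 3 and 4; selection threshold 0.05; 10 or 20 independent candidates, about half categorical. Three of them are prognostic (two continuous, one binary), each correlating r with cognition at every visit. The document gives no r. The allogeneic share of 54/234 = 0.23 comes from annual transplant volume and may differ among eligible survivors.

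**The plan's own figure.** The stated detectable difference of 0.209 cannot be reproduced, because its SD, sidedness and contrast are not given. With SD 1, two-sided, 40 per arm, plausible contrasts give 0.47 (post-baseline mean adjusted for Time 1) to 0.71 (last minus first). So 0.209 would need an SD of about 0.30 to 0.44. It is neither confirmed nor shown wrong, and nothing below uses it.

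**1. What the rule selects.** A t-test flags a continuous variable in 5% of trials. Fisher's exact test flags transplant type in 2.9% at a 23% share (1.7% to 3.3% for shares of 0.1 to 0.5). At least one of the three prognostic variables is flagged with probability 1 − 0.95² × (1 − 0.0286) = 0.12.

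**2. Change contrast (Time 3 minus Time 1).** Variance = 2 × (1 − 0.60) = 0.80. SE = √(0.80 × 2/40) = 0.200. Power = 0.695; detectable difference 0.57 SD. A generalised least squares fit to one simulated complete data set gave estimate 0.6738 and SE 0.200 both without and with three main-effect covariates at r = 0.35. If 13 of 40 per arm are lost after Time 1 (0.68 × 40 ≈ 27 kept), SE = √(2 × [0.64/27 + 0.40²/40]) = 0.2354. The fixed list takes this to 0.2351 (r = 0.20) or 0.2316 (r = 0.35).

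**3. Time 1-adjusted contrast.** Variance = 1 − 0.60² = 0.64. SE = √(0.64 × 2/40) = 0.179. Power = 0.788; detectable difference 0.51 SD. Simulated power, 10,000 runs per row:

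| Candidates | r | Time 1 score only | Rule at 0.05 | Fixed list of three |
|---|---|---|---|---|
| 10 | 0.20 | 0.783 | 0.770 | 0.777 |
| 10 | 0.35 | 0.782 | 0.772 | 0.831 |
| 20 | 0.20 | 0.778 | 0.753 | 0.778 |
| 20 | 0.35 | 0.777 | 0.755 | 0.825 |

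The rule costs 1.0 to 2.5 points against the Time 1 score alone. Its type I error is 0.051. Moving the threshold from 0.05 to 0.10 changes the p < 0.05 verdict in 2.1% to 4.0% of trials. A further run at r = 0.30 gave 0.784 for the Time 1 score alone and 0.809 for the fixed list.

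**4. Why the list gains little at moderate r.** With three covariates the residual variance is (1 − 3r²) − (0.60 − 3r²)²/(1 − 3r²).
- r = 0.20: 0.88 − 0.48²/0.88 = 0.618, against 0.64 with Time 1 alone. Estimating three more coefficients uses up that small gain.
- r = 0.30: 0.73 − 0.33²/0.73 = 0.581.

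**5. Ceiling on r.** Three independent covariates explain 3r² of the variance at every visit. Under AR(1) 0.60 the Time 1 to Time 4 correlation is 0.60² = 0.36. At r = 0.35, 3r² = 0.3675, which leaves a residual covariance of 0.36 − 0.3675 = −0.0075. The limit is r = √(0.36/3) = 0.346, so the r = 0.35 rows are an upper bound.

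**The case against.** The strongest defence is that Aim 2 is about change. Hypothesis 2 speaks of improvement, the Aim 2 text does too, and three of the four earlier results in the Aim 3 power text are time-by-treatment interactions. On a change contrast with complete data the rule costs nothing, and that stands. It is also fair that 0.05 is the only alpha in the document, that the candidate classes are bounded, and that section 7.3 lists seven demographic variables. Still, the contrast is inferred and not stated, the power text speaks of a mean difference between arms, and the 0.05 is never tied to covariate selection. That the study is preliminary does not remove the need, because its estimate is to guide a larger trial.

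A reader might infer four stronger points that the document does not support:

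- *A large power loss on a treatment main effect averaged over all visits.* The remark that "the main effect for treatment was not statistically significant" concerns sleep quality in an earlier study. Averaging Time 1 into the effect is not proposed for cognition.
- *Inflated false positives.* Under a fixed threshold there is no inflation. Choosing the threshold or list after seeing the data is a separate freedom that these figures do not measure.
- *Proof in section 2.1 that time since transplant is prognostic.* That text describes recovery by one year after transplant, whereas eligibility (section 3.2) is 1 to 5 years. It remains only a candidate.
- *Every term other than BMI is chosen by baseline tests.* Phase advance (section 7.3, item 18), light-box duration and expectancy by treatment (section 9.1, Aim 2) follow their own rules.

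**Conclusion.** The point holds as a modest one about pre-specification. Demographic and clinical baseline covariates are selected on chance imbalance without a threshold, and the Aim 2 contrast and Time 1 handling are open. On the change reading, which Hypothesis 2 best supports, the rule does no harm with complete data. On a Time 1-adjusted contrast it costs about 1 to 3 points of power. A fixed list of three covariates gains nothing over the Time 1 score alone at r = 0.20, about 3 points at r = 0.30, and at most about 5 points near r = 0.35. The main gain, about 0.70 to 0.79 in power, comes from adjusting for Time 1 instead of differencing it, not from the covariate list. These sizes rest on the assumed effect, threshold, number of candidates and r. The description of the rule and of the unfixed contrast does not.

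**What to change.** 1. Delete the test-based selection rule from section 9.1 and describe baseline data by arm without significance tests.
2. State the Aim 2 contrast and visit. Enter the Time 1 score as a covariate, or constrain it to a common mean across arms.
3. Before arm-level data are examined, fix a short covariate list on prognostic grounds from variables already collected. It should include BMI, as section 7.3 already says. Time since transplant, age, premorbid ability and transplant type are candidates for the team to judge.
4. Make sections 7.3 and 9.1 agree and refer to each other.

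Possible wording: *Baseline characteristics will be summarised by arm without tests. The Aim 2 contrast is the difference between arms at [visit], with the Time 1 score adjusted for. Models will also include BMI and [list], fixed before arm-level data are examined.*

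The cost is an edit to the analysis text and a few degrees of freedom out of 80 patients. Weak covariates will bring no gain, and if the team keeps a change contrast they bring essentially none, so the list should stay short.
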